## RESEARCH OBJECTIVES AND SPECIFIC AIMS

More than 40% of patients with established heart failure (HF) have diabetes. Several studies have reported that HF patients with diabetes have higher rates of recurrent HF hospitalizations, longer durations of hospital stay, and significantly higher mortality compared to HF patients without diabetes. In a recent 42-month longitudinal study of 902 patients with type 2 diabetes (T2D) and HF, 30% of patients with T2D and HF died and 60% experienced a composite endpoint of death and HF readmission. Despite these statistics, remarkably little is known about optimal strategies for the management of patients with T2D and HF after hospital discharge.

There is strong epidemiologic evidence linking poor glycemic control in patients with T2D with the risk of hospitalization for HF and higher mortality, regardless of ejection fraction. A linear relationship between glycemic control and HF events has been reported across several observational studies in T2D, such that, on average, the risk of HF was increased by 15% for each percentage point higher glycosylated hemoglobin (HbA1c). Several clinical trials using traditional glucose lowering drugs have failed to demonstrate either reduction of new-onset HF or hospitalization rates in patients with established heart disease. More recently, observational and randomized clinical trials in patients with T2D have shown that treatment with sodium glucose co-transporter 2 inhibitors (SGLT2-i) results in a substantial reduction in hospitalization for HF and reduced mortality in patients with established heart disease. The osmotic diuretic effect of SGLT2-i may provide a unique benefit to patients with coexisting T2D and HF, by lowering blood glucose levels and at the same time promoting reduction in plasma volume, weight loss, and lower blood pressure. Additional actions on cardiac metabolism and neurogenic signaling may also contribute to the observed benefits. The beneficial effects with SGLT2-i were present within a few months of commencing therapy and continued with ongoing therapy, suggesting that this therapy may be effective in preventing HF admissions in patients with T2D.

Recent cardiovascular outcome trials using SGLT2-i reported a significant reduction in hospitalization for HF. In the DECLARE trial, dapagliflozin resulted in lower rate of hospitalization for heart failure compared to placebo (HR, 0.73; 95% CI, 0.61 to 0.88). More recently, among patients with heart failure and a reduced ejection fraction (HFrEF), the risk of worsening heart failure or death from cardiovascular causes was lower among those who received dapagliflozin than among those who received placebo, regardless of the presence or absence of diabetes. Similarly, in the EMPA-REG OUTCOME study with empagliflozin, the HR was 0.65 (95% CI 0.50-0.85) and in the CANVAS program with canagliflozin, the HR was 0.67 (95%CI 0.52-0.87). In the Canvas Program, the rate of hospitalization was dramatically lower in patients with history of HF (28.1% vs 14.1%) compared to those without a history of HF (5.7% vs 4.3%). The consistency across trials, as well as the results of observation studies indicate that SGLT2-i will be considered in the management of T2D patients with a history of HF. It will be noted, however, that the time of initiation of SGLT2-i therapy has yet to be formally evaluated in patients with T2D and HF.

We propose to perform a randomized clinical trial to evaluate the effects of dapagliflozin on hospital readmission rates in patients with and without T2D after an admission for acutely decompensated heart failure (ADHF). We hypothesize that treatment with dapagliflozin for 26 weeks will reduce the rate of readmissions for HF (primary endpoint), and will improve glycemic control, HF symptoms, NT proBNP levels, quality of life, resource utilization and hospital charges/costs as compared with placebo.

### Specific Aims:

**Aim 1: To determine whether the composite rate of hospital readmissions, emergency department, urgent clinic visits for HF and death are lower in patients with ADHF treated with dapagliflozin compared to those treated with placebo.** Patients with and without diabetes ADHF will be randomized to receive either dapagliflozin (10 mg once daily) or placebo at hospital discharge for 26 weeks.

**Hypothesis:** Treatment with dapagliflozin will significantly reduce the composite rate of hospital admissions, emergency department visits and urgent clinic visits for HF compared to placebo in patients discharged after an ADHF admission.

[figure not shown]
**Aim 2: To determine whether treatment with dapagliflozin compared to placebo will result in lower HF disease-specific biomarker (NT proBNP), improvement in glycemic control (HbA1c) in T2D patients, and improvement in symptoms and quality of life after hospital discharge in patients with ADHF.** We will measure changes in HbA1c, NT proBNP levels and HF-specific quality of life assessment using the Kansas City Cardiomyopathy Questionnaire (KCCQ) and improvement in symptoms using the Chronic Heart Failure Questionnaire (CHQ-SAS).

**Hypothesis:** Treatment with dapagliflozin will result in a greater improvement in HbA1c levels (in T2D patients), HF disease-specific marker (NT proBNP), quality of life (KCCQ scores), improvement of symptoms (CHQ-SAS scores) compared to placebo after hospital discharge at 12 and 26 weeks.

**Aim 3. Evaluate the within-trial cost-effectiveness of dapagliflozin compared to placebo in overall healthcare costs in patients with ADHF.** We will prospectively collect information on overall health care costs including emergency room visits, urgent clinic visits for HF, and hospitalizations between groups during the 6 months of intervention.

**Hypothesis:** Treatment with dapagliflozin will be associated lower resource utilization and health care costs compared to placebo after hospital discharge.

**Innovation.** The proposed study will be the first prospective RCT to determine the safety and efficacy of dapagliflozin treatment in preventing readmissions/ER visits/urgent clinic visits and death in patients with and without T2D after admission for ADHF. Treatment with SGLT2-i has been shown to reduce both HF hospitalization and mortality in patients with established heart disease and a history of HF . More recently, among patients with HFrEF, dapagliflozin was shown to reduce the risk of worsening heart failure or death from cardiovascular causes compared to placebo, regardless of the presence or absence of diabetes . However, the time of initiation of SGLT2-i therapy has yet to be formally evaluated in patients with ADHF and is the purpose of this study. In addition, we will evaluate the impact of treatment on HF symptoms quality of life, resource utilization and cost-effectiveness of dapagliflozin versus placebo. The results of this study have great potential to influence and facilitate care and to change current clinical guidelines in the management of patients with ADHF.

**Rationale on Dapagliflozin treatment.** Dapagliflozin (Farxiga®) is a highly selective SGLT2-i, given in once-daily doses. It is rapidly absorbed with a time to maximum plasma concentration of two hours and a half-life of 17 hours, with an absolute oral bioavailability of dapagliflozin following the administration of a 10 mg dose of 78%. Dapagliflozin is approximately 91% protein bound. Protein binding is not altered in patients with renal or hepatic impairment. The metabolism of dapagliflozin is primarily mediated by UGT1A9; CYP-mediated metabolism is a minor clearance pathway in humans. Dapagliflozin and related metabolites are mainly eliminated via the renal pathway. The mean plasma terminal half-life for dapagliflozin is approximately 12.9 hours following an oral dose of Farxiga 10 mg.

Clinical trial in ambulatory patients with T2D reported a significant reduction in HbA1c of ~ 0.8%-1.5% from baseline in patients with T2D. Dapagliflozin as monotherapy and in combination with other antidiabetic drugs is well tolerated and associated with very low rates of hypoglycemia. In addition, due to its mechanism of action of increasing urinary glucose excretion, SGLT2-i can reduce systolic blood pressure and body weight compared to placebo in patients with T2D.

In a recent pooled *post-hoc* analysis of completed clinical trials, treatment with dapagliflozin 10 mg produced clinically meaningful reductions in HbA1c and weight vs placebo in patients with concomitant T2DM and HF. In the recent DAPA-HF (Dapagliflozin and Prevention of Adverse Outcomes in Heart Failure) trial, 4474 patients with and without diabetes with New York Heart Association class II, III, or IV heart failure and an ejection fraction of 40% or less assigned to receive either dapagliflozin (at a dose of 10 mg once daily) or placebo, in addition to recommended therapy. The primary outcome was a composite of worsening heart failure (hospitalization or an urgent visit resulting in intravenous therapy for heart failure) or cardiovascular death. Over a median of 18.2 months, the risk of worsening heart failure or death from cardiovascular causes was significantly lower among those who received dapagliflozin than among those who received placebo, regardless of the presence or absence of diabetes. In addition, the trend toward a decrease in systolic blood pressure seen with dapagliflozin occurred without an increase in heart rate. Similar results were also reported in the DECLARE Trial in 17,160 patients with T2D who had or were at risk for atherosclerotic cardiovascular disease treated either with dapagliflozin or placebo. Dapagliflozin resulted in a lower rate of cardiovascular death or hospitalization for HF (4.9% vs. 5.8%; hazard ratio, 0.83; 95% CI, 0.73 to 0.95; P=0.005), which reflected a lower rate of hospitalization for heart failure (hazard ratio, 0.73; 95% CI, 0.61 to 0.88). The results of DECLARE and DAPA-HF trials, together with previous SGLT2-i trials indicate that in patients with and without T2D with or at risk for atherosclerotic cardiovascular disease, treatment with SGLT2-I results in lower rate of cardiovascular death or hospitalization for HF.

### **Study Endpoints:**

**Primary outcome** is to compare the efficacy of dapagliflozin compared with placebo, on the composite rate of hospital admissions, emergency department visits, urgent clinic visits for HF and death after admission with ADHF.

**Secondary outcomes** are to determine differences between dapagliflozin compared to placebo in:

1. Change in the KCCQ score between baseline score and the scores at 12, and 26 weeks
2. Change in the CHQ-SAS score between baseline score and the scores at 12, and 26 weeks
3. Change in NT proBNP levels between baseline and after 12 and 26 weeks
4. Change in 6-minute walk distance (6MWD) between baseline and after 12 and 26 weeks
5. Change in HbA1c between baseline and after 12 and 26 weeks (in T2D patients). [SEP]
6. Change in weight between baseline and after 12 and 26 weeks [SEP]
7. Change in systolic blood pressure between baseline and after 12 and 26 weeks
8. Change from baseline in left atrial volume index and other measures of left ventricular systolic and diastolic function in patients who may undergo repeated echocardiogram during follow up.

## 9. Change from baseline in serum magnesium at baseline and after 12 and 26 weeks

### Safety Variables

1. All-cause mortality
2. Cardiovascular death
3. Non-fatal myocardial infarction (MI)
4. Stroke
5. Acute kidney injury (defined as doubling of serum creatinine based on the RIFLE criteria ).
6. Adverse events (AEs) and serious adverse events (SAEs). Of special interest are events including diabetic ketoacidosis (DKA), volume depletion (defined as hypotension, syncope, orthostatic hypotension or dehydration), hypoglycemic events and urinary tract infections.

### Study Methods:

The trial is a 26-week, randomized, double-blind, placebo-controlled trial investigating the efficacy of dapagliflozin versus placebo in reducing hospital readmission, ER visits, urgent clinic visits for HF and death after discharge, in patients with and without T2D, following an admission with ADHF.

### Patients:

Patients admitted with ADHF will be enrolled after signing an informed consent. Patients will be invited to participate during their hospital admission. Those fulfilling the inclusion/exclusion criteria will undergo baseline testing at randomization prior to discharge.

We will recruit 392 patients, hospitalized with ADHF. Patients with T2D can be treated with diet or oral antidiabetic drugs (OAD) except TZDs, or SGLT2-i, or on low-dose insulin therapy (total daily dose [TDD]  $\leq$ 0.4 unit/kg/day) prior to admission.

### Inclusion Criteria

1. Males or females between the ages of 18 and 90 years, with ADHF, and New York Heart Association (NYHA) class II, III, or IV symptoms discharged after hospital admission with a clinical diagnosis ADHF.
2. Elevated NT-pro-BNP  $\geq$ 300 pg/ml or BNP ( $\geq$ 100 pg/ml) on admission.
3. Interpretable echocardiogram during hospital admission (or within 12 months prior to index hospitalization)
4. Blood glucose level  $<$ 400 mg/dL without evidence of diabetic ketoacidosis (serum bicarbonate  $<$ 18 mEq/L or positive serum or urinary ketones)- Applies to patients with T2D.

### Exclusion Criteria

1. Age  $<$  18 or  $>$  90 years.
2. Subjects with a history of type 1 diabetes.
3. Treatment with TZDs or SGLT2-i during the past 3 months of admission.
4. Recurrent episodes of severe hypoglycemia or hypoglycemic unawareness.
5. History of recurrent HF admissions considered to be due to non-compliance (evaluated by the research staff for participation)
6. Patients with clinically significant hepatic disease (cirrhosis, jaundice, end-stage liver disease, portal hypertension) and elevated ALT and AST  $>$  3 times upper limit of normal.
7. Patients with impaired renal function (GFR  $<$  25 ml/min).
9. Mental condition rendering the subject unable to understand the nature, scope, and possible consequences of the study.
10. Patients on ventricular assist devices (VADs)

11. History of heart transplant or listed for heart transplant
12. History of cardiac surgery\* (within 90 days prior to enrollment) or planned cardiac interventions\* within the following 6 months
 

\*Includes: *PCI, ablation, CRT-ICD*
13. HF due to restrictive/infiltrative cardiomyopathy, active myocarditis, constrictive pericarditis, severe stenotic valvular diseases, hypertrophic cardiomyopathy, or congenital heart disease.
14. History of SGLT2-i allergy
15. Systolic blood pressure < 100 mmHg
16. Uncontrolled hypertension, defined as a systolic blood pressure > 200 mmHg at randomization
17. Female subjects who are pregnant or breast-feeding at time of enrollment into the study.
18. Females of childbearing potential who are not using adequate contraceptive methods (as required by local law or practice).
19. In hospice or expected life expectancy less than 6 months
20. Patients with diabetic foot infection, osteomyelitis, and history of amputation of lower extremities within 6 months of admission
21. Patients anticipated to undergo major surgical procedures during the following 6 months
22. Patients with active hematuria, urinary tract infection (UTI), or history of frequent UTIs or genital mycotic infections
23. Uncontrolled atrial fibrillation or atrial flutter with a resting heart rate >110bpm documented by ECG at randomization.
24. Any condition that in the opinion of the investigator would contraindicate the assessment of 6MWD
25. Chronic pulmonary disease i.e. with known FEV1 <50% requiring home oxygen, or oral steroid therapy or current hospitalization for severe COPD thought to be a primary contributor to dyspnea, or significant chronic pulmonary disease in the Investigator's opinion, or primary pulmonary arterial hypertension
26. Patients with active history of bladder cancer.
27. Patients with previous history of diabetic ketoacidosis, per ADA criteria 

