**Schedule of Assessments:**

Visit		2	3	4	5	6	7	8	9
Screening	Randomization (Discharge) c								
Week	0	0	2	6	8	12	16	20	24
Clinic / CTSA Visit		X	X	X		X		X	X
Phone Visit					X		X		X
Sign Informed Consent	X								
Medical History	X								
Weight, BMI	X	X		X		X		X	X
Physical Exam	X	X		X		X		X	X
Vital Signs	X	X		X		X		X	X
Blood & Urine Sampling a	X	X		X ^		X		X ^	X
Urine Pregnancy Test b	X			X		X		X	X
6-minute Walk Distance			X			X			X
KCCQ Questionnaire		X				X			X
CHQ-SAS Questionnaire		X				X			X
AEs and SAEs		X	X	X	X	X	X	X	X
Electrocardiogram		X d							
Echocardiogram c		X				X			
Review Home BG Testing Results in T2D			X	X	X	X		X	X
Home Urine Ketone Testing, if Indicated			X	X	X	X		X	X
Study Drug Dispensing		X				X			
Study Drug Returned						X			X
T2D Education	X								
Heart Failure Education	X								

aAdmission tests: For screening purposes we will use available laboratory results during current admission (chemistry including eGFR, HbA1c, urine studies), additional testing will be necessary to meet all the baseline lab requirements such as serum magnesium, NT-proBNP, ketones (patients with T2D at investigator's discretion), albumin/creatinine ratio, random urine sodium , at baseline (prior to discharge). Follow up testing at 12 and 26 weeks; other ^blood tests at 6 and 20 weeks and urine culture will be performed at investigator's discretion. bUrine pregnancy test for women with childbearing potential at investigator's discretion c Echocardiogram during hospital admission (or within 6 months prior to index hospitalization) and at 12 weeks follow up visit. All visits have a +/-7-day visit window. d the most current ECG during admission. e Randomization can be performed prior to discharge or up to 7 days after discharge (if discharge planning over the weekend. \*\*COVID-19: For modified study visit options applicable during the time period of the COVID-19 emergency, please see appendix B.

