### **Withdrawal Criteria**

1. The subject may withdraw at will at any time.
2. The subject may be withdrawn from the trial at the discretion of the investigator due to a safety concern or if judged non-compliant with trial procedures or included in contravention to the inclusion and/or exclusion criteria.
3. Adverse events (AE), i.e., any clinical, laboratory abnormality or concurrent illness which, in the opinion of the investigator, indicates that continued participation in the study is not in the best interest of the patient.
4. Doubling of serum creatinine above the baseline value confirmed by a repeated measurement within one week (study medication can be discontinued and continue study visits as described in the premature treatment discontinuation).
5. Pregnancy or intention to become pregnant.

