**Acute kidney injury and impairment in renal function.** There have been reports of acute kidney injury in patients receiving SGLT2-I. Dapagliflozin should be avoided during prolonged fasting or fluid losses (such as gastrointestinal illness). SGLT2-i may increase serum creatinine and decreases eGFR. Patients with moderate renal impairment (eGFR less than 25 mL/min/1.73 m^2) should not be started on dapagliflozin.

**Lower limb amputation.** An increased risk for lower limb amputation (primarily of the toe) has been observed in clinical studies with SGLT2-I therapy. In the recent DECLARE study, the rate of non-traumatic lower limb amputations was not increased compared to placebo treatment. Patients at increased risk of amputations including such as a history of prior amputation and diabetic foot ulcers will not be enrolled in this trial.

**Changes in serum magnesium.** Recent reports and a meta-analysis of 18 RCTs involving 15,309 patients provided evidence that SGLT2 inhibitors significantly increase serum magnesium levels in patients with T2D. On average, serum magnesium levels were raised by 0.04-0.06 mmol/l for all SGLT2-I agents indicating a drug class effect. The mechanisms are not completely understood, but likely relates to SGLT2 i- induced glucosuria and osmotic diuresis. The significant elevations in serum magnesium levels are not known, with some studies reporting an association between high magnesium levels and total mortality in individuals with heart failure and those receiving hemodialysis. However, in the general population and in people with type 2 diabetes, high end of the normal range of serum magnesium has been associated with a lower risk of cardiovascular events, lower systolic BP by 2.00 mmHg and diastolic BP by 1.78 mmHg compared with placebo. It has been hypothesized that a modest increase in serum magnesium could have contributed to a reduction in cardiovascular mortality observed among participants with type 2 diabetes in the EMPA-REG OUTCOME trial.

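### The renal exclusion carries no time point and may be met on any eGFR from the admission, so the written procedure does not catch a patient who is below the protocol's own limit when study drug starts

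*Combined protocol and SAP*

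**What the plan says.** **Eligibility.** Exclusion Criteria, item 7, begins "Patients with impaired renal function (GFR" and gives a limit of less than 25 ml/min. It states no date and no source for the value. In the same list, item 16 (systolic pressure above 200 mmHg) and item 23 (heart rate in atrial fibrillation or flutter) are tied to randomization.

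**Source of the value.** Footnote a of the Schedule of Assessments says: "For screening purposes we will use available laboratory results during current admission (chemistry including eGFR, HbA1c, urine studies". It continues: "additional testing will be necessary to meet all the baseline lab requirements such as serum magnesium, NT-proBNP, ketones". The rest of that list adds albumin/creatinine ratio and urine sodium. It does not name serum creatinine or eGFR.

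**Order of steps.** The Patients section says: "Those fulfilling the inclusion/exclusion criteria will undergo baseline testing at randomization prior to discharge". The schedule marks "Blood & Urine Sampling" at both Screening and Randomization. Measurements During follow-up, item 13, says that clinical chemistry is collected according to the study plan.

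**Start of drug.** Treatment Protocol places the start at discharge, after standard inpatient heart failure treatment that includes diuretics. Footnote e allows randomization up to 7 days after discharge. The kidney paragraph under Potential risks associated with dapagliflozin use says that patients with eGFR below 25 "should not be started on dapagliflozin".

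**Rules that need a reference creatinine.** Withdrawal Criteria, item 4: "Doubling of serum creatinine above the baseline value confirmed by a repeated measurement within one week". Renal disorders: a re-test when creatinine is at least 50% above baseline. Safety Variables, item 5: "Acute kidney injury (defined as doubling of serum creatinine based on the RIFLE criteria". None of the three says which sample is the reference.

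**A different renal exclusion.** Hypoglycemia risk protection says that chronic kidney disease beyond stage II is excluded.

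**The concern.** The protocol uses one number, 25, for two purposes: to decide who enters and to say who should not begin the drug. The two moments differ. Entry may rest on a value from any day of the admission. The first dose comes after days of decongestive treatment, and possibly after a further week at home. Creatinine can move in either direction over that time, so an early value above 25 does not establish that the limit is met when treatment begins.

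At stake is a safety criterion that the written steps do not enforce at the moment to which the protocol itself attaches it. The date also matters because the Renal disorders section gives a separate instruction for an eGFR that falls below 25 on treatment. Which instruction applies depends on whether the fall came before or after the first dose, and no eligibility check is placed at that boundary.

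A smaller matter is that the doubling rule, the 50% re-test rule and the acute kidney injury variable all depend on a baseline creatinine that is never identified. With several sites, the choice could differ from one to another.

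**Working it through.** The plan states no figure on this point, so there is nothing to reproduce. The main check is a comparison of sections. The arithmetic only shows how much the date of the sample can matter.

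**1. Sequence as written**

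- Screening: item 7 is judged, and footnote a accepts any eGFR from the admission.
- Eligibility is met, and then baseline testing is done at randomization (Patients section).
- Drug starts at discharge. If randomization is delayed under footnote e, the start is later still.
- No section says that the randomization sample is compared with 25, or that its result must be known before dosing.
- The statement on not starting below 25 is in the risk section, with no test, date or step attached.

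The limit on starting is therefore stated, but no step carries it out.

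**2. How large a creatinine change crosses the limit**

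Assumption, not from the documents: eGFR is proportional to creatinine to the power -k, with k between 1.0 and 1.2. The factor needed to reach 25 is (eGFR / 25)^(1/k).

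| Qualifying eGFR | k = 1.2 | k = 1.0 |
|---|---|---|
| 30 | (30/25)^(1/1.2) = 1.16 | 30/25 = 1.20 |
| 35 | (35/25)^(1/1.2) = 1.32 | 35/25 = 1.40 |
| 40 | (40/25)^(1/1.2) = 1.48 | 40/25 = 1.60 |

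A patient who qualifies at 30 reaches the limit with a rise in creatinine of 16% to 20%. One who qualifies at 40 needs 48% to 60%. The documents give no distribution of admission eGFR or of inpatient change, so these figures say nothing about frequency.

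**3. What an undefined baseline could do to the creatinine rules**

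Let r = discharge creatinine / the creatinine used as baseline. The documents give no values of r; the range 0.7 to 1.5 is assumed. The rise over the discharge value needed to trigger a rule is 2/r for doubling and 1.5/r for the 50% re-test.

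| r | Doubling (2/r) | 50% re-test (1.5/r) |
|---|---|---|
| 0.7 | 2.86 | 2.14 |
| 0.8 | 2.50 | 1.88 |
| 1.0 | 2.00 | 1.50 |
| 1.25 | 1.60 | 1.20 |
| 1.5 | 1.33 | 1.00 |

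If creatinine fell during admission (r below 1) and the earlier value is the baseline, the rules respond too late. If it rose (r above 1), they respond too early; at r = 1.5 the re-test rule is met with no change after dosing. This applies only if a site uses an earlier admission value. With the randomization sample taken at discharge, r is 1.

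**The case against.** Two stronger readings are tempting, and the documents support neither.

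- A reader might infer that the plan permits starting drug below 25. It does not. The risk section says that such patients should not be started, and no section says otherwise. The plan fails to catch these patients; it does not approve them.
- A reader might infer that kidney injury will be judged against an outdated creatinine. The text points the other way. Footnote a limits admission results to screening, the Patients section puts baseline testing at randomization before discharge, the schedule marks blood sampling there, and item 13 of the measurements list has chemistry follow the schedule. The list in footnote a is open-ended, so the absence of creatinine from it proves little. An earlier value being used is possible, but the plan does not state it.

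Other points on that side are fair in part. Item 15 (systolic pressure below 100) and the liver enzyme limit in item 6 are also undated, and blood pressure from the day of screening may decide eligibility, so judging criteria at screening is the protocol's general habit. That weakens the contrast with items 16 and 23. It does not remove the mismatch for the renal limit, which the protocol itself attaches to starting the drug.

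Acute kidney injury is a safety variable, and under blinded randomization an unclear baseline should affect both arms alike. The doubling rule requires a confirmatory repeat, and the re-test rule leads to investigator judgment. These points limit the consequence of the baseline question. Whether the cited RIFLE source fixes a reference creatinine cannot be checked from the documents.

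**Conclusion.** The eligibility point holds. Item 7 is undated, footnote a accepts any eGFR from the admission, baseline testing follows the eligibility decision, and no step applies the limit again before the first dose. The written procedure therefore does not deliver the protocol's own statement about starting the drug.

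Its size is unknown. The 16% to 60% changes in creatinine rest on an assumed power relation and chosen starting values. They show that the limit can be crossed, not how often it is. The primary comparison is not affected.

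The baseline creatinine point holds only as a request for clarification. The natural reading is the randomization sample, and the protocol needs to say so.

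The exclusion of kidney disease beyond stage II conflicts with the limit of 25 and must be reconciled with it. This review takes no view on which renal limit is right.

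**What to change.** 1. Reconcile the Patients section, Exclusion Criteria item 7, footnote a of the Schedule of Assessments and the kidney paragraph of the risk section, so that the existing renal limit is checked on the most recent eGFR before randomization. Keep earlier admission chemistry for pre-screening only.
2. Reconcile these with the stage II kidney disease exclusion under Hypoglycemia risk protection, so that the protocol states one renal criterion.
3. As a secondary clarification, confirm that the chemistry sample already scheduled at randomization is the baseline creatinine meant in Withdrawal Criteria item 4 and Renal disorders, and the reference for acute kidney injury in Safety Variables item 5.

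No renal limit or withdrawal rule changes. The cost is a few lines of text and the need to have the eGFR result in hand before randomizing; blood is already scheduled at that visit. Patients whose eGFR fell below the limit during admission would no longer qualify. Their number cannot be estimated from the documents.
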